2.3 Exploratory Objectives & Endpoints

Exploratory objectives will include the following:

- 2.3.1 Describe pharmacodynamics (PD) effects of alisertib in peripheral blood and/or bone marrow samples.

Serial blood and/or bone marrow samples will be collected at specific timepoints. Flow cytometry, colony forming assays, AURKA autophosphorylation assays, and in vitro cultures of patient specimens to assess the effect of MLN8237 on megakaryocytes and other hematopoietic cells will be measured.

- 2.3.2 Evaluate the relationship between biomarker expression levels and response to alisertib.

Changes in biomarker expression levels from baseline will be measured (using PD samples) to correlate with response to alisertib therapy. Biomarkers will include a) genes encoding key enzymes in Aurora kinase signaling, b) markers of cellular aneuploidy and apoptosis, and c) markers of megakaryocytic differentiation.

- 2.3.3 Evaluate reduction in splenomegaly by palpation (MF arm only).

Patients will be examined for splenomegaly by palpation once per cycle and change from baseline will be calculated over time.

- 2.3.4 Evaluate improvement in MF symptoms (MF arm only), as assessed by the Myeloproliferative Neoplasm Symptom Assessment form (MPN-SAF).

The MPN-SAF will be administered to patients in the MF arm only once per cycle. Changes in symptom scores over time will be calculated.

- 2.3.5 Assess change in bone marrow fibrosis in patients in the MF arm. Bone marrow will be assessed at screening and after cycle 6 in this population.

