10.1.3 Exploratory Endpoints

To describe pharmacodynamic effects, serial measures of megakaryocytes and other hematopoietic cells will be summarized using descriptive statistics such as means, medians and ranges for each time point. These measures will be plotted

for each patient, and these patient specific plots will be plotted for all patients together. Analyses for change over time will be done using repeated measures general linear model analysis.

To evaluate the relationship between biomarker expression levels and response, changes in biomarker expression levels will be related to response using a Wilcoxon rank sum test. To evaluate reduction in splenomegaly by palpation in the MF arm, a categorical variable measuring the extent of splenomegaly will be tracked over time descriptively, since the small sample size will preclude longitudinal analysis. To evaluate improvement in MF symptoms in the MF arm, the Myeloproliferative Neoplasm Symptom Assessment (MPN-SAF) score will be summarized descriptively over time using means, medians, standard errors and ranges.

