Appendix II – Revised IWG-MRT & ELN Response Criteria for MF

The criteria below are a revision of the International Working Group-Myeloproliferative Neoplasms Research and Treatment (IWG-MRT) criteria for treatment response in myelofibrosis (MF) and represents a collaborative effort by the IWG-MRT and the European LeukemiaNet to objectively assess the value of new drugs in inducing morphologic remission or improvement in MF-associated symptomatic burden (MF-SB).

Response Categories	Required Criteria ¹
CR (complete remission)	
 Bone marrow²: age-adjusted normocellularity; < 5% blasts; ≤ grade 1 MF³ Peripheral blood: hemoglobin ≥ 100 g/L and < ULN; neutrophil count ≥ 1 × 10⁹ and < ULN Platelet count ≥ 100 × 10⁹ and < ULN; < 2% immature myeloid cells⁴ Clinical: resolution of disease symptoms; spleen and liver not palpable; no evidence of EMH.
PR (partial remission)	
 Peripheral blood: hemoglobin ≥100 g/L and <UNL; neutrophil count ≥1 × 10⁹/L and <UNL; platelet count ≥100 × 10⁹/L and <UNL; <2% immature myeloid cells⁴ and Clinical: Resolution of disease symptoms; spleen and liver not palpable; no evidence of EMH or Bone marrow²: Age-adjusted normocellularity; <5% blasts; ≤grade 1 MF³, and peripheral blood: Hemoglobin ≥85 but <100 g/L and <UNL; neutrophil count ≥1 × 10⁹/L and <UNL; platelet count ≥50, but <100 × 10⁹/L and <UNL; <2% immature myeloid cells⁴ and Clinical: Resolution of disease symptoms; spleen and liver not palpable; no evidence of EMH
Clinical improvement (CI)	The achievement of anemia, spleen or symptoms response without progressive disease or increase in severity of anemia, thrombocytopenia, or neutropenia ⁵
Anemia response	
 Transfusion-independent patients: a ≥ 20 g/L increase in hemoglobin level⁶ Transfusion-dependent patients: becoming transfusion independent⁷
Spleen response ⁸	
 A baseline splenomegaly that is palpable at 5-10 CM, below the LCM, becomes not palpable⁹ 
OR
 
 A baseline splenomegaly that is palpable at > 10 cm, below the LCM, decreases by ≥ 50% 
A baseline splenomegaly that is palpable at <5 cm, below the LCM, is not eligible for spleen response

Symptoms response	A ≥ 50% reduction in the MPN-SAF TSS ¹⁰

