Progressive disease ¹¹	
 Appearance of a new splenomegaly that is palpable at least 5 cm below the LCM or A ≥100% increase in palpable distance, below LCM, for baseline splenomegaly of 5-10 cm or A 50% increase in palpable distance, below LCM, for baseline splenomegaly of >10 cm or Leukemic transformation confirmed by a bone marrow blast count of ≥20% or A peripheral blood blast content of ≥20% associated with an absolute blast count of ≥1 × 10⁹/L that lasts for at least 2 weeks
Stable disease	Belonging to none of the above listed response categories.

Relapse	
 • No longer meeting criteria for at least CI after achieving CR, PR, or CI, or • Loss of anemia response persisting for at least 1 month or • Loss of spleen response persisting for at least 1 month
Recommendations for assessing treatment-induced cytogenetic and molecular changes	
Cytogenetic remission	
 • At least 10 metaphases must be analyzed for cytogenetic response evaluation and requires confirmation by repeat testing within 6 months window 
CR: eradication of a preexisting abnormality PR: ≥50% reduction in abnormal metaphases
 
Partial response applies only to patients with at least ten abnormal metaphases at baseline.

Molecular remission	
 • Molecular response evaluation must be analyzed in peripheral blood granulocytes and requires confirmation by repeat testing within 6 months window • CR: Eradication of a pre-existing abnormality • PR: ≥50% decrease in allele burden 
Partial response applies only to patients with at least 20% mutant allele burden at baseline.

Cytogenetic/molecular relapse	Re-emergence of a pre-existing cytogenetic or molecular abnormality that is confirmed by repeat testing.

EMH, extramedullary hematopoiesis (no evidence of EMH implies the absence of pathology- or imaging study-proven nonhepatosplenic EMH); LCM, left costal margin; UNL, upper normal limit.

¹ For all response categories, benefit must last for ≥12 wk to qualify as a response.

² Baseline and posttreatment bone marrow slides are to be interpreted at one sitting by a central review process. Cytogenetic and molecular responses are not required for CR assignment.

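### Section 10.1.3 summarises spleen size only as an undefined category and does not carry through the change from baseline promised in 2.3.3

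*Combined protocol and SAP*

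**What the plan says.** Section 2.3.3 sets the exploratory spleen endpoint for the MF arm: "Patients will be examined for splenomegaly by palpation once per cycle and change from baseline will be calculated over time". It names no unit.

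Section 10.1.3 gives the only analysis of that endpoint: "a categorical variable measuring the extent of splenomegaly will be tracked over time descriptively", "since the small sample size will preclude longitudinal analysis". The categories are not defined there or elsewhere.

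The same section treats its other repeated measures differently. For the pharmacodynamic measures, "Analyses for change over time will be done using repeated measures general linear model analysis". The MPN-SAF "score will be summarized descriptively over time using means, medians, standard errors and ranges".

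Appendix II works in centimetres below the left costal margin (LCM). One arm of its spleen-response rule reads "A baseline splenomegaly that is palpable at > 10 cm, below the LCM, decreases by ≥ 50" percent, and one of its progression criteria is a "50% increase in palpable distance, below LCM, for baseline splenomegaly of >10 cm". Footnote 9 bases confirmation of spleen response on palpation, or on ultrasound where body habitus prevents palpation.

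**The concern.** The endpoint and its analysis do not match. A reader of 2.3.3 expects a change from baseline for each patient over time. A reader of 10.1.3 finds a category with no levels, so two analysts could build different tables and both would comply with the plan.

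What is at stake is how well a partial spleen reduction can be seen in at most 24 patients. A coarse category hides any reduction that stays within one level, and it can turn a trivial change across a boundary into an apparent improvement. No other analysis in Section 10 clearly makes up for this, as the working shows.

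**Working it through.** The plan states no sample size, precision or power figure for the spleen endpoint, so there is none to reproduce. The check sets the texts side by side and then illustrates the loss.

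**1. Does the stated reason support categorising?** A small sample can rule out a longitudinal model. It does not rule out subtracting a baseline value from a later one. If change in cm were summarised by a mean, the 95% confidence half-width in units of the standard deviation (SD) of change is t(0.975, n−1)/√n:

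| n | Half-width (SD units) |
|---|---|
| 24 | 0.42 |
| 18 | 0.50 |
| 12 | 0.64 |
| 6 | 1.05 |

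The documents give no SD, so these cannot be turned into centimetres. The intervals are wide for small n but can be reported, and individual trajectories need no minimum n. Section 10.1.3 already summarises MPN-SAF numerically in the same patients.

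**2. Is the measurement needed anyway?** Yes. The Appendix II spleen-response and splenic-progression rules cannot be applied without the palpable distance. The Section 5.1 schedule lists palpation at screening, C1D1 and day 1 of cycles 2 to 6: 1 + 1 + 5 = 7 assessments, with an eighth at C7D1 if the patient attends. After cycle 6, stable MF patients attend every second cycle. Section 4.2 says odd cycles and footnote m of Section 5.1 says even cycles.

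**3. Does another analysis in Section 10 report a partial spleen reduction?** Section 10.1.2 reports two proportions: PR or better, and PR or better together with stable disease. Appendix II places spleen response under clinical improvement and defines stable disease as meeting none of the listed categories. Read literally, a patient whose best result is clinical improvement through the spleen is in neither proportion. Even if such a patient were counted in the second proportion, the spleen reduction would not be identifiable. Patients with a baseline spleen under 5 cm cannot have a spleen response at all.

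**4. Illustration of the loss.** The plan defines no categories. Assume the Appendix II baseline bands: not palpable, under 5, 5–10, over 10 cm.

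- 18 to 11 cm: (18 − 11)/18 = 39% reduction. Both values exceed 10 cm, so no change is shown.
- 24 to 12 cm: (24 − 12)/24 = 50% reduction, which meets the response threshold if it lasts the 12 weeks required by footnote 1. Both values exceed 10 cm, so no change is shown.
- 10.5 to 9.5 cm: 1/10.5 = 9.5% reduction. The band changes, so an improvement is shown.

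Under the same bands, assume baseline length uniform from 5 cm to an upper limit U, and a common reduction r. A patient stays in band if the baseline lies between 5/(1−r) and 10, or above 10/(1−r). For r = 0.30 and U = 20 the share is [(10 − 7.14) + (20 − 14.29)]/15 = 57%. In full:

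| Reduction | U = 20 cm | U = 25 cm |
|---|---|---|
| 20% | 75% | 81% |
| 30% | 57% | 68% |
| 40% | 33% | 50% |
| 50% | 0% | 25% |

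The cut-points and the baseline distributions are both assumptions.

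**5. An alternative coding.** If the category were instead the Appendix II outcome (response, no response, progression), 24 to 12 cm would register as a response and 10.5 to 9.5 cm would not. The change from 18 to 11 cm would still show nothing, because 39% is below 50%.

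**The case against.** The best defence is that 2.3.3 names no scale. A category compared with its baseline level is formally a change from baseline, and 10.1.3 says its aim is to evaluate reduction. On that reading the two sections are mismatched and underspecified, not contradictory. This stands, and the point should not be put as a contradiction.

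A reader might also infer that centimetre data collected every cycle are being thrown away. The documents do not support that. No section says outright that centimetres are recorded at each palpation; 2.3.3 and Section 5.1 refer only to palpation, and the unit is inferred from Appendix II. Stable patients are not seen every cycle after cycle 6. Any centimetre value recorded still feeds the Appendix II response and progression rules and is missing only from the 10.1.3 summary.

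The illustration is also open to challenge. In Appendix II the bands are baseline strata that decide which response rule applies. The plan does not adopt them as on-treatment categories, and the alternative coding removes two of the three examples.

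Finally, percent change is undefined when the spleen is not palpable at baseline, and MF eligibility in Section 3.2 does not require splenomegaly. A recommendation of percent change for every MF patient would fail, so the fix restricts it.

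None of this supplies the missing category definition or explains why a small sample calls for categories.

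**Conclusion.** The point holds in limited form. Section 10.1.3 leaves its spleen variable undefined and omits the change from baseline named in 2.3.3, and its stated reason justifies avoiding a model but not categorising. These conclusions rest on the text alone.

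The size of the loss cannot be fixed, because the plan gives neither categories nor a baseline distribution. Under the assumed bands a 30% reduction would leave 57% to 68% of patients in the same category, and a 50% reduction 0% to 25%. Other cut-points would give other figures.

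The consequence is confined to an exploratory, descriptive endpoint in a pilot whose primary objective is safety. Alpha, power, and the primary and secondary conclusions are untouched. It is worth correcting because 10.1.3 is the only place in Section 10 where, on a literal reading, a spleen reduction short of PR would be reported.

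**What to change.** Amend Section 10.1.3 as follows.

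- State that the palpable distance in cm below the LCM is recorded at each scheduled palpation.
- Summarise absolute change from baseline at each visit for all MF patients, and percent change only for those with a palpable spleen at baseline. Show individual trajectories. No longitudinal model is needed.
- Report the Appendix II spleen-response proportion among MF patients with a baseline spleen of at least 5 cm. Handle splenectomised patients by footnote 8 and ultrasound-confirmed cases by footnote 9.
- If categories are kept, define them in advance and present them as a supplement.

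The cost is a little more descriptive output and an edit to the text. The eCRF is not among the documents. If it does not already capture centimetres at each palpation, one field must be added, and Appendix II could not be applied without it in any case.

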4.0 TREATMENT PLAN

4.1 Overview

This will be a two arm pilot study of alisertib treatment in patients with AMKL or MF. The starting dose (level 1) for all patients will be 50 mg BID, administered orally on days 1-7 of each cycle (1 cycle = 21 days), based on the MTD from previous studies. Patients may continue to receive cycles of alisertib until progression of disease or unacceptable toxicity. There will be no long-term follow-up beyond end of treatment, aside from a standard end of treatment visit approximately 30 days after the last dose of study drug, followed by a final off-study visit approximately 6 months after the last dose. Patients with on-going adverse events will be followed until resolution of the event(s), defined as a return to baseline or stabilization of the event.

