4.6 Duration of Therapy

Patients may continue to receive alisertib treatment until any of the following occur:

- Disease progression
- Development of an inter-current illness that prevents further administration of treatment
- Unacceptable adverse event(s)
- Patient decides to withdraw from either study treatment or the as a whole study
- The treating investigator determines that the patient should be taken off treatment for any reason (i.e. changes in condition, inability to comply with study treatment or procedures)

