- ^g Disseminated intravascular coagulation (DIC) screen should include: PT/INR, aPTT, fibrinogen, and D-dimer. Cycle 1 day 1 PT/INR/aPTT does not need to be performed if the screening DIC was within 3 days of this visit. If the initial DIC is positive follow-up coagulation studies should include the full DIC panel (rather than the PT/INR/aPTT alone). See footnote t.
Note: Beyond Cycle 6, PT/INR, aPTT testing is not required.
- ^h Serum pregnancy test required for women of child-bearing potential during screening AND pre-dose on Cycle 1 day 1. Results must be available and negative prior to dosing. See footnote t.
- ⁱ It is strongly preferred that correlative samples be collected and shipped only on Monday – Thursday (with same day shipment preferred). Friday collections/shipments should be avoided to ensure sample stability. Since these samples are collected on Day 1 of each cycle, it is preferred that Day 1 visits be conducted on Monday through Thursday when correlative samples are being collected. Sites should use the available windows to achieve this. Please contact the QAM if there are any questions
- ^j Peripheral blood (25 ml) and/or bone marrow (bone marrow only if done clinically – will collect about 10-20 ml) samples will be collected for determination of alisertib pharmacodynamics (PD studies). Blood samples will be collected at the start of each cycle (D1). Sample collection at D15 will be optional. (Samples will be collected for a maximum of 6 cycles). Correlative bone marrow samples should be obtained any time bone marrows are collected as clinically indicated during study participation. . At baseline, correlative bone marrow collection is not mandatory for study entry. However, study team should request 3-4 unstained slides from any prior bone marrow testing performed within the last year before study entry. Please refer to laboratory manual for details.
- ^k Bone marrow aspirate and biopsy is required within 1 year prior to registration (provided the PI confirms the diagnosis and there is no suspicion for acceleration to blast phase), on C7D1 (+/-14 days) and thereafter only as clinically indicated.
- ^l Palpation for splenomegaly and MPN-SAF will be done only on MF patients. Baseline MPN-SAF and palpation for Splenomegaly within 14 days of registration

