(Note: The original criteria mandates the use of imaging studies where a $\geq 35\%$ reduction in spleen volume, as assessed by MRI or CT, is required. Furthermore, a $\geq 35\%$ volume reduction in the spleen or liver, by MRI or CT, constitutes a response regardless of what is reported with physical examination.)

- ¹⁰ Symptoms are evaluated by the MPN-SAF TSS.¹⁷ The MPN-SAF TSS is assessed by the patients themselves and this includes fatigue, concentration, early satiety, inactivity, night sweats, itching, bone pain, abdominal discomfort, weight loss, and fevers. Scoring is from 0 (absent/as good as it can be) to 10 (worst imaginable/as bad as it can be) for each item. The MPN-SAF TSS is the summation of all the individual scores (0-100 scale). Symptoms response requires $\geq 50\%$ reduction in the MPN-SAF TSS.
- ¹¹ Progressive disease assignment for splenomegaly requires confirmation by MRI or computed tomography showing a $\geq 25\%$ increase in spleen volume from baseline. Baseline values for both physical examination and imaging studies refer to pretreatment baseline and not to posttreatment measurements.

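### The MF symptom analysis summarises MPN-SAF scores among patients still on treatment, not within-patient change, so the average can move with who remains

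*Combined protocol and SAP*

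**What the plan says.** Section 2.3.4 makes improvement in MF symptoms an exploratory objective. On collection it says "The MPN-SAF will be administered to patients in the MF arm only once per cycle", and on analysis "Changes in symptom scores over time will be calculated". It does not say whether the change is within-patient, from which baseline, or in which patients.

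Section 10.1.3 opens its sentence with "To evaluate improvement in MF symptoms in the MF arm" and then says that the MPN-SAF "score will be summarized descriptively over time using means, medians, standard errors and ranges". It mentions no change from baseline, number contributing, fixed cohort or rule for missing scores. The same section relates changes in biomarker levels to response and plots pharmacodynamic measures patient by patient. MPN-SAF gets neither treatment.

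In the MF schedule of events (Section 5.1), MPN-SAF is marked at screening, Cycle 1 Day 1, Day 1 of Cycles 2-6 and Day 1 of Cycle 7 onward. The cells for the end-of-treatment (EOT) and end-of-study (EOS) visits are blank.

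Appendix II defines a symptoms response as a reduction of at least 50% in the MPN-SAF total symptom score (TSS, 0 to 100). Its footnote 1 requires benefit in any response category to last at least 12 weeks. A symptoms response counts only towards clinical improvement. Section 10.1.2 reports two proportions, at least PR and at least PR or stable disease, and neither isolates symptom response.

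**The concern.** A mean of scores at each cycle answers a question about improvement only if the same patients contribute throughout. Here they need not. Treatment continues until progression, intercurrent illness, unacceptable toxicity, withdrawal or an investigator decision (Section 4.6), and no score is scheduled afterwards. Each later mean is therefore taken over a smaller group that may differ from the group at baseline. Movement in that mean combines change within patients with change in who is left.

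Section 1.1.2 describes the goals of non-transplant treatment in MF as palliative and directed at symptoms, so readers will look at this result even though it is exploratory. A falling average could be read as relief when no patient has improved.

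**Working it through.** **No figure to reproduce.** The documents give no expected MPN-SAF mean, SD, dropout rate or link between symptoms and stopping. The check asks whether the effect can occur and how large it is over a stated range of assumptions.

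**Who contributes.** Section 10.1.3 does not limit the summary to patients on treatment. That follows from the schedule, because a patient who stops has no further planned score. Section 4.2 and footnote m of Section 5.1 also have stable MF patients attend every second cycle after Cycle 6, with only CBC and CMP in between. That sits uneasily with once-per-cycle collection and changes the contributing group again. (The two places also disagree on whether the clinic cycles are odd or even, and need reconciling.)

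**Arithmetic example (assumed scores).** Take 24 MF patients, the maximum allowed, four at each of 10, 20, 30, 40, 50 and 60. Nobody's score changes.

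- Baseline mean = (10+20+30+40+50+60)/6 = 35; median 35.
- The 4 highest leave: mean (10+20+30+40+50)/5 = 30; median 30.
- The 8 highest leave: mean (10+20+30+40)/4 = 25; median 25.
- The 12 highest leave: mean (10+20+30)/3 = 20; median 20.

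The paired change is 0 in every case. The median moves as much as the mean, so reporting both gives no protection. If the 16 who stay after the 8 highest leave each worsen by 3 points, the observed mean goes from 35 to 28 while the paired change is +3.

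**Weaker links between score and leaving.** Let f be the fraction leaving, ρ the correlation between the score and the tendency to leave, and z the standard normal point with upper tail f. With normal scores and no within-patient change, the large-sample shift in the mean is −ρ × SD × φ(z)/(1 − f).

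- f = 0.25: 0.318/0.75 = 0.424. From ρ = 0.3, SD 10 to ρ = 0.8, SD 20, the fall is 0.3 × 10 × 0.424 = 1.3 to 0.8 × 20 × 0.424 = 6.8 points.
- f = 0.5: 0.399/0.5 = 0.798. The same range gives 0.3 × 10 × 0.798 = 2.4 to 0.8 × 20 × 0.798 = 12.8 points.

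A simulation of 20,000 trials of 24 patients, with no true change, gives slightly smaller shifts, as expected at this sample size:

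| SD | ρ | 25% leave | 50% leave |
|---|---|---|---|
| 10 | 0.3 | −1.21 | −2.30 |
| 10 | 0.5 | −2.04 | −3.90 |
| 10 | 0.8 | −3.25 | −6.19 |
| 15 | 0.3 | −1.83 | −3.44 |
| 15 | 0.5 | −3.07 | −5.81 |
| 15 | 0.8 | −4.88 | −9.31 |
| 20 | 0.3 | −2.46 | −4.59 |
| 20 | 0.5 | −4.09 | −7.69 |
| 20 | 0.8 | −6.52 | −12.36 |

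At ρ = 0 every shift is within 0.04 points of 0.

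**The case against.** **The plan already promises changes.** Sections 2.3.4 and 10.1.3 can be read together: changes are calculated and scores are also summarised. This is fair, and the two sections should not be called contradictory. But Section 10.1.3 is where the analysis is specified, and it does not say that changes are paired, from which baseline, or with how many patients. The gap is one of specification.

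**Appendix II already gives a within-patient symptom measure.** It does, and responses are to be categorised by those criteria. No planned proportion reports symptom response, however, so the measure would be derived without necessarily being shown.

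**No passage shows that more symptomatic patients leave.** This stands. A reader might infer that the planned means will lose the sickest patients. The documents do not support that: MF progression in Appendix II rests on spleen size and blasts, and no stopping reason in Section 4.6 is defined by symptom score. A link is plausible, because the side effects in Section 8.1.10 overlap with TSS items (fatigue, fever, abdominal discomfort), but it remains an assumption.

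**The endpoint is exploratory, descriptive and uncontrolled.** This also stands. No test, threshold or primary or secondary conclusion depends on it, and without a control arm symptom change could not be attributed to alisertib even with complete data. That sets the priority; it does not remove the problem.

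**Conclusion.** The point holds as a minor-priority improvement. The planned summary of MPN-SAF levels, joined to a schedule that stops collecting when treatment stops, can show a fall in mean and median with no within-patient improvement. The size depends on assumptions that the documents do not supply: about 1 to 12 points for SD 10 to 20, 25% or 50% leaving and correlation 0.3 to 0.8, and about 0 if leaving is unrelated to score.

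A reader might go further and expect a fall of about 11 points: 0.545 SD × 20 = 10.9, the result if exactly the worst-scoring third leaves. That needs a perfect link between score and leaving plus an assumed SD and dropout fraction, none of which the documents give. It is an extreme illustration and should not be quoted as the expected bias.

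The consequence is limited to how an exploratory result is interpreted. The primary safety analysis and the planned response proportions are unaffected.

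**What to change.** 1. In Section 10.1.3, state that within-patient change in MPN-SAF TSS from baseline will be summarised at each cycle, with the number of patients contributing. Name the baseline: the schedule marks both screening and Cycle 1 Day 1, and footnote l uses the term for the score within 14 days of registration. Paired change removes the artefact shown above, but still describes a selected group of patients who remain, and should be labelled so.
2. Report the Appendix II symptom response (at least 50% TSS reduction, lasting at least 12 weeks) as a proportion of all treated MF patients with a baseline score. Count missing assessments as non-response and state that this is conservative.
3. Optionally, add MPN-SAF at the existing EOT visit. Report it separately, because it falls about 30 days after the last dose and does not repair the on-treatment cycle summaries.

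No model is needed. The cost is a few sentences in Section 10.1.3, slightly more analysis, a more conservative response figure and, if the third item is adopted, one questionnaire at a visit already held.
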